11.1.1.3. Post-emergency phase

Once the emergency phase is over and treatment has been delivered, we will seek full written informed consent as soon as practical. For most patients this means within 12 hours of admission. This consent will be a two parts process:

- We will seek consent to allow use of data already acquired during the emergency phase

b) We will seek consent for ongoing participation in the study.

Written Informed Consent will be obtained by means of participant dated signature and dated signature of the person who presented and obtained the Informed Consent. The person who obtained the consent must be suitably qualified and experienced, and have been authorised to do so by the Chief/Principal Investigator. A copy of the signed Informed Consent will be given to the participant and another copy will be filed in their medical records. The original signed form will be retained at the trial site.

If the participant elects to withdraw from the study at this point then we will present them with three withdrawal options as outlined in section 11.2.1.

If a patient is unable to provide informed consent at this stage due to deterioration in clinical condition, then advice may be sought from a relative/carer/friend acting as a consultee. When reasonable steps have been taken to identify a consultee and one is unavailable, then the researcher must nominate a person to act as in their stead. This person may be involved in the patient's care in a professional capacity but they must have no connection with the research project. A suitable person who might act as a nominated consultee is an independent doctor working with the patient or nominated by the healthcare provider. Consent from the patient will be obtained directly, if they recover promptly, at the earliest opportunity.

11.2. Discontinuation/Withdrawal of Participants from Trial Treatment

11.2.1. Study Withdrawal

We anticipate and have made provision for withdrawal when the emergency exception period is complete; if a patient is assessed and has capacity then they may completely or partially withdraw at any time. This possibility will be made clear as a part of seeking of full written informed consent after the initial emergency procedure. Participants may have the following three options for withdrawal:

- 1) Participants may withdraw from active follow-up and further communication but allow the trial team to continue to write to their GP and access their medical records and any relevant hospital data that is recorded as part of routine standard of care; i.e., Radiology/diagnostic test, blood results and disease progression data etc.
- 2) Participants can withdraw from the study but permit data obtained up until the point of withdrawal to be retained for use in the study analysis. No further data would be collected after withdrawal.
- 3) Participants can withdraw completely from the study and withdraw the data collected up until the point of withdrawal. The data already collected would not be used in the final study analysis.

The type of withdrawal and reason for withdrawal will be recorded in the case report form (CRF).

If the participant is withdrawn due to an adverse event, the Investigator will arrange for follow-up visits or telephone calls until the adverse event has resolved or stabilised.

11.2.2. Participant death

If the participant dies before giving full written consent then we propose to continue using the data obtained. We would not seek further 'consent' from relatives at the risk of causing undue distress.

11.3. Recruitment

RETRIEVE-AMI is a multi centre study recruiting at the John Radcliffe Hospital and the Newcastle upon Tyne Hospitals NHS Foundation Trust sites. Participants will be identified as they are being admitted for primary PCI. They will be approached by a research team member (a primary PCI operator who is also a member of the clinical care team) who will verbally assent them as explained in section 11.1.1.1. Upon assent, participant will be randomised to one of the three study arms, by a system based on sealed Envelope system. Consent will be completed at the post-emergency phase as described in section 11.1.1.3.

11.4. Randomisation

Date and version No:22/04/2024 v4.0

Upon assent, participant will be randomised to one of the three study arms, by a system based on sealed envelopes. Randomization will take place in the cathlab once both inclusion and exclusion criteria are verified and assent provided.

11.5. Blinding and code-breaking

Due to the interventional nature of the trial, masking and code-breaking procedures are not applicable.

11.6. Study timeline

Stage 1 – Screening, Assent & Randomisation

Participant identification and assent will proceed as described in sections 10 and 11.1.1.1-11.1.1.2 respectively.

- Diagnostic angiography will be performed in the standard manner using appropriate catheters. Heparin will be administered as routinely used for PCI. Angiograms will be reviewed to ensure participation eligibility according to angiographic inclusion/exclusion criteria (section 10.3)
- Once eligibility is confirmed patients will be assented and randomised.

Stage 2 – Baseline assessments

- Once the lesion has been crossed with a coronary guidewire, flow will be established with a 1.5mm semicompliant balloon predilation.
- OCT measurements will be performed using a dedicated OCT catheter over the coronary guide wire in the usual manner for clinical OCT assessment. For Arm 1, the OCT measurements in the baseline assessment will be treated as the pre-stent measurements as thrombus modification will not be performed in this group.

Stage 3 – Post-thrombus modification pre-stent assessments

Patients randomised to Arm 2 (thrombus aspiration) or Arm 3 (thrombus retrieval) will undergo the assessments in this stage.

- Thrombus aspiration (Arm 2) will proceed according to standard clinical practice. In brief, a thrombus aspiration device (i.e. Export Catheter) will be advanced over the coronary guidewire. Aspiration will then proceed.

Date and version No:22/04/2024 v4.0

- Retrieval thrombectomy (Arm 3) will proceed according to the manufacturer's manual. In brief, a microcatheter (e.g. Phenom™, Marksman™) is advanced over the guidewire. Once the microcatheter has traversed the thrombotic occlusion the Solitaire™ X revascularisation device is advanced through the microcatheter until the usable length of the stent extends past each side of the thrombus in the vessel. Then the microcatheter is retracted to the proximal radiopaque marker of the stent. As this retraction occurs the stent self-expands and entangles the thrombus. Next, the microcatheter and Solitaire™ X Revascularisation Device are withdrawn as a unit into the guide catheter under continuous aspiration (Appendix C).
- OCT measurements will be performed using a dedicated OCT catheter over the coronary guide wire in the usual manner for clinical OCT assessment.
- Angiography-derived coronary physiology measurements will be performed with up to two angiographic views (complementary and separated by an angle of at least 25 degrees) at a frame rate of 15 frames per second. Maximal hyperaemia will be achieved with an intravenous infusion of adenosine at a rate of at a rate of 140 mg/kg/min. Since stage 3 is the same as stage 2 for Arm 1 participants, these measurements will be performed at Stage 2.
- Extracted thrombus from aspiration/stent retriever at any stage of the procedure will be collected, and imaged *ex-vivo*.

Stage 4 – PCI & post-PCI assessments

- PCI will proceed according to clinical practice. Post-dilation will be performed at the operator's discretion.
- OCT measurements will be performed following a successful angiographic PCI result using a dedicated OCT catheter over the coronary guide wire in the usual manner for clinical OCT assessment.
- Angiography-derived coronary physiology measurements will be performed with up to two angiographic views (complementary and separated by an angle of at least 25 degrees) at a frame rate

of 15 frames per second. Maximal hyperaemia will be achieved with an intravenous infusion of adenosine at a rate of at a rate of 140 mg/kg/min.

Stage 5 – Consent & data collection

Patients will be approached for consent according to procedures detailed in section 11.1.1.3. Once consent has been obtained in-hospital data collection will be completed (section 11.7.1.). ECGs will also be stored.

Stage 6 – 6 month follow-up

At 6 months patients will have a scheduled telephone follow-up to gather relevant clinical information as detailed in section 11.8.

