8. OBJECTIVES AND OUTCOME MEASURES

Objectives	Outcome Measures	Timepoint(s) of evaluation of this outcome measure (if applicable)
Primary Objectives		
Efficacy of thrombus burden reduction	Thrombus volume (mm ³) (OCT assessment)	Pre-stent
Safety of retriever thrombectomy	
Angiography-/OCT-defined device related target vessel complications, device deficiencyRate of major adverse cardiac and cerebrovascular events (MACCE)	Pre-stent In hospital 30 days 6 months
Secondary Objectives		
Efficacy of thrombus burden reduction	Thrombus area, flow area (mm ²) (OCT assessment)	Pre-stent
Efficacy of thromboatheroma reduction	Thromboatheroma area, flow area (mm ²) (OCT assessment)	Post-stent
Efficacy of stent implantation	Stent expansion & apposition (OCT assessment)	Post-stent
Angiographic success rate	TIMI flow, Myocardial Blush Grade, Angiography derived coronary physiology indices	Post-stent

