11.7.3. Angiography-derived coronary physiology

Coronary physiology measurements during emergency PCI can be used to assess the coronary microvascular function which is affected amongst other factors by the pre-stenting thrombotic burden and distal embolisation of atherothrombotic material during angioplasty.³ Indeed, coronary physiology measurements under adenosine-induced hyperaemia can be employed to characterise microvascular obstruction and predict the extent of myocardial infarction.²¹ Contemporary work enables us to derive cardiac physiology indices such as quantitative flow ratio non-invasively using coronary angiograms.^{22,23}

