12.1.3. Investigational arm (Arm 3)

Participants randomised to the stent-retriever thrombectomy arm of the RETRIEVE AMI trial will undergo stent-retriever thrombectomy with the Solitaire™ X Revascularisation Device (Figure 3). The Solitaire™ X revascularisation device has been clinically approved and CE marked for use in acute ischaemic stroke endovascular intervention.¹⁴ Solitaire™ X works by mechanically retrieving the thrombus and restoring blood flow to the area distal to the occlusion. The Solitaire™ X Revascularisation Device is a self-expanding stent designed for dynamic clot integration with radiopaque markers that enhance visualisation of the optimal working length. Features including the range of stent diameters and usable lengths are presented in Appendix B. The device can be used in

vessels with a diameter between 2.0mm and 5.5mm at the thrombotic occlusion site (Appendix B).

Figure 3: Solitaire™ X device

After a thrombotic occlusion has been identified and crossed with a guidewire, the stent-retriever thrombectomy proceeds as described below (see Appendix C for schematic diagram).¹⁵ A microcatheter (e.g. PhenomTM, MarksmanTM) is advanced over the guidewire. Once the microcatheter has traversed the thrombotic occlusion the SolitaireTM X revascularisation device is advanced through the microcatheter until the usable length of the stent extends past each side of the thrombus in the vessel. Then the microcatheter is retracted to the proximal radiopaque marker of the stent. As this retraction occurs the stent self-expands and entangles the thrombus. Finally, the microcatheter and SolitaireTM X Revascularisation Device are withdrawn as a unit under continuous aspiration into the guide catheter. PCI will then proceed with devices and techniques driven by clinical decision making at the patient level and institutional level, and carried out in accordance with local guidelines.

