17. PROTOCOL DEVIATIONS

A trial related deviation is a departure from the ethically approved trial protocol or other trial document or process or from Good Clinical Practice (GCP) or any applicable regulatory requirements. Any deviations from the protocol will be documented in a protocol deviation form and filed in the trial master file.

All deviations will be reported to the MHRA.

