19.6. Possible risks/discomfort to participants

Patients referred for emergency cardiac catheterization and PCI will undergo this procedure as would routinely be performed. Patients will therefore be informed of the standard of care procedure and its associated risks. All local protocols will be adhered to and only fully trained staff will carry out procedure according to departmental SOPs.

From a research perspective, the PCI procedure time may be lengthened by around 10 minutes to complete the selected study procedures (OCT acquisitions, angiography derived physiology & aspiration/stent retriever thrombectomy). In the context of a PCI procedure that typically lasts approximately 60 minutes. The additional time should not result in any clinically significant difference to the participants. Very occasionally this additional time can result in some back discomfort for patients having to lie on the angiography bed for the additional time period.

Stent-retriever thrombectomy with the Solitaire X revascularisation device is clinically tested and licensed for endovascular intervention in acute ischaemic strokes. Device failure was reported in one case (0.8%) in the two trials that examined this endpoint with no significant sequelae. Device related complications such as arterial dissection or perforation was reported in 5/211 (2.3%) of ischaemic stroke patients randomised to stent-retriever thrombectomy with the Solitaire X revascularisation device. Perforations and edge dissections are encountered in routine PCI practice in 0.37% and 7.7% of patients and interventional cardiologists are familiar with their management. Coronary perforations and significant

Clinical Trial Protocol Template version 15.0

CONFIDENTIAL

© Copyright: The University of Oxford and Oxford University Hospitals NHS Foundation Trust 2019

Page 47 of 57

Date and version No:22/04/2024 v4.0

dissections are usually treated with a stent which is the treatment these patients will eventually receive for their heart attack.

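### Section 11.6 prints the intravenous adenosine rate as 140 mg/kg/min in two places, an implausible unit that nothing else in the protocol corrects; check the source PDF and amend if it reads mg

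*Combined protocol and SAP*

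**What the plan says.** Section 11.6 (Study timeline) describes angiography-derived physiology at two points. Under Stage 3, before stenting, it states: "Maximal hyperaemia will be achieved with an intravenous infusion of adenosine at a rate of at a rate of 140 mg/kg/min". Arm 1 has no thrombus-modification step, so its first measurement is moved to Stage 2. The same sentence, with the same doubled phrase, is printed again under Stage 4, after PCI. Every arm is therefore covered, at two measurements per participant.

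The other places that could bear on the dose are these:

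- Section 11.7.3 explains the purpose of the measurement: "coronary physiology measurements under adenosine-induced hyperaemia can be employed to characterise microvascular obstruction". It gives no dose.
- Section 12.3 (Other Interventions) is marked as not applicable.
- Section 19.6 counts the measurement among the research procedures: "the PCI procedure time may be lengthened by around 10 minutes to complete the selected study procedures (OCT acquisitions, angiography derived physiology". It does not mention adenosine. It also says: "All local protocols will be adhered to and only fully trained staff will carry out procedure according to departmental SOPs".
- Section 8 lists the secondary outcome that the Stage 4 measurement serves: "TIMI flow, Myocardial Blush Grade, Angiography derived coronary physiology indices", assessed post-stent.
- Heparin, the other drug in Section 11.6, has no numeric dose: "Heparin will be administered as routinely used for PCI".

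**The concern.** A rate in milligrams per kilogram per minute, with 140 in front of it, means grams of an intravenous drug every minute. That is implausible on its face for a diagnostic infusion in a patient with an acute myocardial infarction. The sentence is an operative instruction and not background text, and it is the only numeric drug dose in the protocol. A reader therefore has no second figure to check it against. The protocol gives no maximum dose and no infusion duration.

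Participant safety is at stake first: a protocol used at two sites should not carry a dosing unit that staff have to recognise as wrong and disregard. A smaller matter is that the hyperaemic condition for one component of a secondary outcome is not correctly specified.

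**Working it through.** **Inputs.** The rate, 140 mg/kg/min, is from Section 11.6. Body weight is not in the documents, so 50, 70 and 100 kg are assumed. The planned number randomised, 81, is from the Synopsis and Section 14.1. The plan derives no total dose, so there is no figure of its own to reproduce.

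**Step 1: the rate as printed.** Dose per minute = rate × weight.

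| Assumed weight | 140 mg/kg/min × weight | In grams |
|---|---|---|
| 50 kg | 7,000 mg/min | 7.0 g/min |
| 70 kg | 9,800 mg/min | 9.8 g/min |
| 100 kg | 14,000 mg/min | 14.0 g/min |

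Without a weight assumption, 140 mg per kg is 140 / 1,000,000 = 0.014% of body mass per minute. No duration is stated, so a total dose cannot be computed.

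**Step 2: the rate if micrograms were meant (assumption).** 140 micrograms/kg/min × 50, 70 and 100 kg = 7.0, 9.8 and 14.0 mg/min. This is 1,000 times less than printed.

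**Step 3: reach of the instruction.** There are two measurements per participant. If all 81 have both, that is 81 × 2 = 162 occasions.

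**Step 4: does another section correct it?** Sections 11.7.3, 12.3 and 19.6 and the amendment history in Appendix D contain no adenosine dose, unit or correction.

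**Step 5: could the unit be an artefact of converting the PDF to text?** The evidence points both ways.

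- Against an artefact: the Greek letters α and β in Section 14.1 and χ in Section 14.2 came through intact, and mg is printed in both places. The doubled phrase suggests the sentence was not proofread, so an authoring slip is credible.
- For an artefact: no micro sign appears anywhere in the text, so there is no direct test of how that character would have been read. The second sentence looks like a copy of the first and is not independent confirmation. Symbols do not render uniformly: trademark signs are printed in Section 11.6, while Section 12.1.3 has "A microcatheter (e.g. PhenomTM, MarksmanTM) is advanced over the guidewire". This last item is weak, because spelling out a symbol as two letters is not the same as replacing one letter by another.

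On balance a misread is less likely than a genuine misprint, but it is not ruled out.

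**The case against.** The strongest reply is that no error in the plan has been established. The finding turns on one character that cannot be verified from extracted text, and a conversion artefact is not a fault in the protocol. That stands, and it is why the conclusion is conditional and the first action is to look at the PDF.

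The second reply is that trained staff would never give this rate. Section 19.6 supports it: adherence to local protocols, departmental SOPs and fully trained operators make literal administration unlikely. That also stands. It limits the likely consequence of the misprint but does not correct it, since those safeguards work here only if staff depart from what Section 11.6 says.

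Four stronger readings are tempting, and the documents do not support them.

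- A reader might infer that participants were exposed to gram doses. Nothing in the documents shows what rate anyone received.
- A reader might infer that sites are trapped between an implausible dose and a regulatory report, because Section 17 says: "All deviations will be reported to the MHRA". That section concerns deviations in general. Nothing shows that an evident unit misprint would be handled that way, and Section 19.6 also commits sites to local procedures.
- A reader might try to prove that the infusion is physically undeliverable by converting it to a fluid volume. That needs a solution strength, and the documents give none.
- A reader might infer that the physiology outcome is invalid. The protocol does not fix which index will be used. Section 11.7.3 offers quantitative flow ratio, derived from angiograms, as an example, and nothing says how any index depends on the adenosine rate.

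**Conclusion.** Wrong as written, conditional on the source PDF reading mg. As printed, the rate is 7.0 to 14.0 g/min at assumed weights of 50 to 100 kg, at two measurements in every arm, and nothing elsewhere in the protocol corrects it. The arithmetic is certain given the printed unit. The judgement that the rate is implausible rests on its scale, because the documents contain no reference dose. For the same reason, micrograms is the likely intention but remains an assumption.

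This is a cheap safety correction. It does not rank as an essential fix until the character has been confirmed, because literal administration is unlikely and only one component of a secondary outcome is touched. The OCT thrombus-volume endpoint, the sample size and the control of Type I error are unaffected.

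**What to change.** 1. Check the unit in the source PDF at both places in Section 11.6. If it shows a micro sign, no action is needed.
2. If it reads mg, verify the intended rate against the product information and each site's catheter laboratory procedure. Correct the unit under Stage 3 and Stage 4 by amendment, remove the doubled phrase, and notify both sites.
3. If the infusions are already complete (the Synopsis plans an end date of 30/09/2025), correct the record and confirm the rate actually given.

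The cost is one look at the PDF and, if the misprint is confirmed, one unit changed in two places and a notice to two sites. Sample size, primary endpoint and analysis do not change.

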11.7. Trial Assessments

11.7.1. Data Collection, Patient Reported Outcomes and Clinical Outcomes

Data on the clinical procedures and any devices and/or imaging technologies used will be collected. Medical history will be taken from the patient once informed consent has been given and relevant sections of the medical notes and scans may be accessed by the study team. Clinical outcomes and MACCE will be ascertained at the 6-month telephone follow-up, by accessing relevant sections of the medical records or by contacting the GP if appropriate.

11.7.2. Optical Coherence Tomography

OCT is a high-resolution intravascular imaging modality that can accurately characterise coronary plaque morphology and quantify atherothrombotic burden.^{4,19} It also has the capability to accurately define the inner lumen of the native coronary artery allowing to measure the flow area and monitor the structural integrity of the artery. It is expected therefore to play a key role in identifying target vessel complications (e.g. dissection, intramural haematoma) and aspects of stent deployment (e.g. stent apposition, expansion, edge dissection).²⁰ Finally, OCT has the advantage of having a fast acquisition frame rate and being relatively inexpensive.

